5.2 Study Plan and Procedures

Study RBUS with UJA will be obtained within 10 days following CT diagnosis of ureteral calculus. Ureteral jet data will be documented and patients will be followed prospectively for 42 days at 2 weeks, 4 weeks and 42 days (6 weeks) after diagnostic CT. Specifically, patients will be followed for spontaneous stone passage and will be expected to record date of stone retrieval. If specific date of stone passage is not known, date of standard of care imaging confirming absence of stone(s) will be used as the date of stone passage. If spontaneous stone passage is not achieved, patients will be counseled regarding further standard of care treatment options including surgical stone removal. If surgical intervention is indicated, time to surgical procedure will also be recorded. This patient cohort will be analyzed retrospectively to determine whether RBUS with UJA is predictive of spontaneous stone passage versus need for surgical intervention over a 42-day period.

Interpretation of RBUS and UJA:

Abdominal radiologists will interpret the RBUS research reads. All grey scale and color Doppler examinations will be performed by means of a commercially available unit with a 1-5 MHz phased array transducer or a 1-6 curved transducer. Flow toward the transducer is assigned a red color on Doppler. For grey scale evaluation, the presence or absence of urinary tract stones, size (longest axis in mm) and location- R, L, upper pole, interpolar and lower pole of the kidneys, proximal ureter, distal ureter and bladder- will be documented. The level of the renal pelvis represents the interpolar kidney with upper and lower pole above and below this level. For this study, a urinary tract stone will be termed an echogenic focus that demonstrates either posterior acoustic shadowing and or twinkle artifact on color Doppler images. In addition, presence of hydronephrosis (mild, moderate, and severe) will be documented. For the purpose of this read, hydronephrosis will be defined as such: mild hydronephrosis - urine fills the intra and extra renal pelvis and the major calyces are dilated; moderate hydronephrosis – above + dilatation of the minor calyx with preservation of the renal parenchyma; severe hydronephrosis – above +

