thin renal parenchyma. In addition, the presence or absence of hydroureter (proximal ureter, above the iliac bifurcation and distal ureter, below the iliac bifurcation) will be documented. If there is a stone in the renal pelvis, it will be recorded as interpolar kidney and noted as renal pelvis. For any case, if the reader believes that a particular stone is the cause of the participant's symptoms, then this will be noted. This is particularly useful in cases in which there are multiple stones. The bladder will be examined in the transverse plane at the level of the trigone to view both jets simultaneously. All participants will be scanned for 5 minutes. The number of jets from each ureteral orifice will be tabulated over time so that ureteral jet frequency, defined as number of jets per minute, can be calculated. Patients will be categorized into three groups. Group I- no ureteral jets on the symptomatic side; Group II- continuous low-level ureteral jet on the symptomatic side; Group III- ureteral jets similar to nonsymptomatic side.

In order to determine if RBUS with UJA along with clinical data confers non-inferior information compared to non-contrast CT, objective findings such as laboratory data including BMP, CBC, urine analysis and physical exam obtained as part of routine care will be retrieved from the patient's medical record and reviewed retrospectively. Clinical data and RBUS results will be de-identified/coded and the Urologist will be blinded to the CT results. Diagnosis and treatment recommendations will be determined based upon these findings and compared to those attained by CT to assess for congruence. Statistical analysis will be performed to determine non-inferiority between the studies.

Stone size and location based on CT will be recorded at the time of enrollment into the study and time to stone passage will be recorded. All study participants will be followed for stone passage. Time to stone passage will be stratified according to stone location (proximal, mid or distal ureter) and size (<2mm, 2-4mm, 5mm, 6-7mm, 9-10mm).

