5.3 Study Follow-up

After study RBUS is obtained, patients will be followed prospectively by telephone call at 2 weeks, 4 weeks and 42 days (6 weeks) from the time of diagnostic CT. They will be followed for spontaneous stone passage, and be asked to keep record of when this occurs. During the 42-day follow up, their course will also be monitored for ED visits, surgical intervention and hospital admissions. All currently available medical records such as Clindesk, Allscripts, Compass, HMED will be reviewed retrospectively to follow participants' clinical course, specifically to determine the need for surgical intervention or spontaneous stone passage. Billing records may also be used to identify patients who underwent surgical intervention based on CPT codes. Evaluation of the patient's emergency room records with a focus on their presenting symptomatology and initial evaluation by the emergency provider will be performed. Any additional laboratory tests and/or imaging obtained during their emergency room or office visit will also be reviewed and collected for study purposes.

Surgical intervention, including ureteral stent or nephrostomy tube placement, ureteroscopy/laser lithotripsy, or extracorporeal shockwave lithotripsy (ESWL) will be instituted, as per standard of care. A follow up telephone call at 2 weeks, 4 weeks and 42

days (6 weeks) from the time of diagnostic CT will be performed in case of care received outside of the Barnes-Jewish Hospital (BJH) system and medical records reviewed for ER visits, hospital admissions and surgical intervention.

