7.0 STATISTICAL CONSIDERATIONS

7.1 Study Objectives and Endpoints

Primary Outcome:

To determine if RBUS with UJA is prognostic of stone passage versus need for

surgical intervention:

1. Passage of stone as assessed by patient self-report and/or collection of stone or imaging.
2. Need for further medical attention as collected by chart review and phone interview for ED visit, hospitalization, or need for surgical intervention during the 42-day follow-up period.

Secondary Outcomes:

1. To determine if RBUS with UJA, in conjunction with standard of care laboratory data and history and physical confers non-inferior information compared to non-contrasted CT:
 - a. Urologist will review the patient's de-identified/coded history and physical, laboratory studies, and RBUS with UJA and make an assessment and treatment recommendations. The urologist will be blinded to the results of the CT. Comparison will be made between the CT diagnosis and the blinded assessment of the urologist.
2. To determine if the natural history and rate and time of stone passage for ureteral stones of differing locations (proximal, mid or distal ureter) and sizes (<2mm, 2-4mm, 5mm, 6-7mm, 9-10mm):
 - a. Assessment of the stone location and size to be conducted by a radiologist.

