7.3 Data Analysis

Primary objective:

This patient cohort will be analyzed retrospectively to determine whether US with UJA is predictive of spontaneous stone passage versus need for surgical intervention. Kaplan-Meier curve will be used to test time to spontaneous stone passage between the two groups. A chi-square test of independence will be used to test intervention rates between the two groups. A multivariate analysis will also be conducted controlling for such variables as age, gender, BMI, side, size of stone, and stone passage. A Cox-proportional hazards model will be used for time to spontaneous stone passage and logistic regression will be used for intervention.

Due to the unforeseen difficulty of recruitment and the uncertain assumptions of the initial power analysis, an interim statistical analysis is recommended to be performed when the recruitment reaches 50 patients. Based on the results, a decision will be made whether to continue recruitment to the initial 100 targeted patients, adjust the number of targeted patients based on a new power analysis, or to discontinue recruitment. The interim results

should not affect primary independent variables in the study as the radiologist performing the ultrasounds will not have access to the results.

Secondary objective 1:

Statistical analysis will be performed to determine diagnostic and treatment concordance between the two methods. A multivariate logistic regression model will also test patient factors that are associated with discordant results.

Secondary objective 2:

In a prospective manner, they will be followed to determine the natural history of ureteral stones with regard to stone passage. Average time to stone passage for each size category and stone location will be determined. Cox-proportional hazard models will be used to determine significant factors affecting time to stone passage.

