APPENDIX A: Study Schedule of Events

		Post-Enrollment Assessment and Follow-up		
		Within one day of diagnostic CT	2 weeks post diagnostic CT (+/- 2 days)	4 weeks post diagnostic CT (+/- 2 days)
Informed Consent	X			
Incl./Excl. Criteria Confirmation	X			
RBUS with UJA	X			
Demographics¹	X			
Medical & Surgical History¹	X			
Height & Weight¹	X			
Basic metabolic panel¹	X			
Complete blood count¹	X			
Urine analysis and microscopy¹	X			
CT scan¹	X			
Assessments:				
Study related AEs/reportable events		X	X	X
Clinical stone management¹		X	X	X
Passage of stone		X	X	X

¹ as part of standard clinical care.

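### Section 7.3 adjusts the primary objective's Cox and logistic models for stone passage, which is itself primary outcome 1

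*Combined protocol and SAP*

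**What the plan says.** Section 7.3, under the primary objective, gives one list of adjustment variables: "A multivariate analysis will also be conducted controlling for such variables as age, gender, BMI, side, size of stone, and stone passage". The next sentence names the models: "A Cox-proportional hazards model will be used for time to spontaneous stone passage and logistic regression will be used for intervention". Nothing limits any listed variable to one of the two.

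Section 7.1 makes passage the first primary outcome: "Passage of stone as assessed by patient self-report and/or collection of stone or imaging". Section 5.2 treats it as a follow-up event: "Specifically, patients will be followed for spontaneous stone passage and will be expected to record date of stone retrieval". In Appendix A the row "Passage of stone" is marked at the follow-up contacts and not in the baseline column. Section 2.1 sets passage against surgery as the two outcomes to be predicted. No text defines stone passage as a baseline variable.

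**The concern.** An outcome has been placed among the covariates of the models meant to predict it. If the list is applied as written, neither model answers the primary question, which is whether the jet finding predicts passage rather than surgery.

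The unadjusted Kaplan-Meier and chi-square comparisons are not touched. They cannot show, however, whether jets tell the clinician anything beyond stone size, and section 1.2 itself expects size to affect passage. Under the primary objective only the adjusted models can show that. Secondary objective 2 also plans Cox models ("Cox-proportional hazard models will be used to determine significant factors affecting time to stone passage"), but names no covariates for them.

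**Working it through.** **Inputs.** From the documents: the covariate list and the two models (7.3), the outcomes (7.1), 42 days of follow-up, and about 100 participants (7.2). The documents give no event rates, jet-group sizes, alpha or effect size, so there is no planned figure to reproduce. Assumed below: two jet groups split 50/50, two-sided 5% alpha, and outcome splits written as passed/surgery/retained at 42 days (%), weak or absent jets against normal jets.

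**Cox model: the mechanism needs no assumed rates.** Let g be the jet group with coefficient β, and let γ be the coefficient of stone passage. Every event is a passer, so each event contributes

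exp(βg_i + γ) / [Σ over passers at risk exp(βg_j + γ) + Σ over non-passers at risk exp(βg_k)].

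Dividing through by exp(γ) gives each non-passer a weight proportional to exp(−γ). The likelihood rises as γ grows, so γ diverges and the non-passers drop out of every risk set. What remains is the Cox model fitted to passers only. It asks how fast stones passed among those that did pass.

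**Cox model: size.** Take constant hazards over 42 days, with surgery as censoring. The total cumulative hazard is L = −ln(proportion retained), and the passage part is L × passed/(passed + surgery).

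- Split A, weak or absent: L = −ln 0.20 = 1.609; passage part 1.609 × 40/80 = 0.805.
- Split A, normal: L = −ln 0.10 = 2.303; passage part 2.303 × 70/90 = 1.791.
- Hazard ratio without stone passage: 0.805/1.791 = 0.449.

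Among passers, times follow a truncated exponential with the total rate L, so the fit with stone passage reflects total exit rates rather than passage rates. Solving the passers-only score equation by numerical integration gives the last column.

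| Split | Weak or absent | Normal | HR without | HR with |
|---|---|---|---|---|
| A | 40/40/20 | 70/20/10 | 0.449 | 0.842 |
| B | 45/40/15 | 75/20/5 | 0.425 | 0.768 |
| C | 40/35/25 | 70/10/20 | 0.525 | 0.945 |
| D | 40/50/10 | 70/10/20 | 0.727 | 1.190 |
| E | 20/50/30 | 50/30/20 | 0.342 | 0.902 |
| F | 20/30/50 | 50/20/30 | 0.322 | 0.878 |
| G | 60/25/15 | 85/10/5 | 0.500 | 0.768 |
| H | 60/30/10 | 80/10/10 | 0.750 | 1.000 |
| I | 50/30/20 | 60/25/15 | 0.751 | 0.930 |

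Split H vanishes because both groups retain 10%, so L is equal. Split D reverses because L is larger with weak or absent jets (2.303 against 1.609).

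**A false effect is also possible.** With equal passage hazards and a surgery hazard eight times higher with weak or absent jets (about 44/51/5 against 70/10/20), the hazard ratio goes from 1.00 to 1.41. In 2,000 simulated trials of 100, the rejection rate rises from 5% to 27%. The rounded percentages themselves give 0.985 rather than exactly 1.00.

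**Cox model with all listed covariates.** Simulated trials of 100 used jet, age, sex, BMI, side and size. Reported here is the setting with size log-HR −0.5 per SD for passage and +0.5 for surgery, and stones 0.5 SD larger with weak or absent jets.

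| Split | Median HR without → with | Rejection rate without → with |
|---|---|---|
| A | 0.45 → 0.75 | 77% → 15% |
| B | 0.41 → 0.68 | 89% → 26% |
| C | 0.52 → 0.93 | 59% → 8% |
| D | 0.74 → 1.16 | 20% → 11% |

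In all 12,000 trials (12 settings × 1,000) the jet coefficient and its standard error matched the passers-only fit to within 1e-8. The passage coefficient was about 21 with standard error about 3,300.

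A separate simulation under different assumptions (40% weak or absent jets, 600 trials per scenario, jet term only) agreed. A true hazard ratio of 0.5 became 0.80 to 0.99, 0.4 became 0.83, and power fell from 0.45–0.91 to 0.05–0.13.

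**Logistic model.** If no passer has an intervention, stone passage separates the data and the jet odds ratio comes from non-passers alone. For split A, without the term it is (40/60)/(20/80) = 2.67; among non-passers it is (40/20)/(20/10) = 1.00. Some passers may have an intervention, since the plan counts "Surgical intervention, including ureteral stent or nephrostomy tube placement". The model then converges.

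| Split | OR without → with, no overlap | OR without → with, 10% of passers have an intervention |
|---|---|---|
| A | 2.67 → 1.00 | 2.12 → 1.00 |
| B | 2.67 → 0.67 | 2.11 → 0.80 |
| C | 4.85 → 2.80 | 3.12 → 1.98 |
| D | 9.00 → 10.00 | 5.73 → 4.27 |

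With all listed covariates at 10% overlap, the medians are 2.23 → 1.05, 2.24 → 0.82, 3.48 → 2.26 and 6.45 → 4.89. At 10% overlap the odds ratio shrinks, moves to 1 or reverses in all nine splits. Among the nine it grows only in D at zero or near-zero overlap (8.48 → 8.73 at 1%; 8.02 → 7.73 at 2%). In the equal-passage-hazard case it also grows at low overlap (9.37 → 20.40 at 0%, 7.28 → 8.90 at 5%).

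**The case against.** The strongest reply is that this is a drafting slip. CT location is recorded beside size at enrolment ("Stone size and location based on CT will be recorded at the time of enrollment into the study"), is paired with size throughout secondary objective 2, and is missing from the list; medical history is also collected at baseline, so prior stone passage could have been meant. Either reading is plausible. The documents support neither explicitly, an analyst cannot choose between them, and under both the line still needs correcting.

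The list is worded as examples, and the term may have been meant for the logistic model only. Open wording lets variables be added; it does not withdraw one that is named. In the logistic model alone the term would still condition on a competing outcome.

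An analyst may well notice a Cox coefficient of about 21 with a standard error of about 3,300, or a separated logistic fit. That has force. But the jet estimate beside the extreme Cox term looks normal, and the logistic model gives no warning once a few passers have an intervention.

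Finally, every rate is assumed, and the logistic distortion is smaller at higher overlap: at 30%, C goes from 1.97 to 1.62 and D from 3.63 to 2.71. Higher overlap is possible, because 7.3 does not define intervention and primary outcome 2 includes ED visits and admissions. This limits what can be said about size. It does not alter the mechanism.

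**Conclusion.** The concern holds: section 7.3 as written is wrong and must be corrected before the adjusted models are run. That the Cox jet estimate reduces to the passers-only estimate is exact, whatever the event rates. The logistic model conditions on an outcome that competes with its own, and it either separates or converges to a distorted odds ratio.

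The usual result under the assumed splits is a jet effect shrunk towards no association. Reversal, and a false effect where passage hazards are equal, are also possible. The figures show mechanism and direction; they are not the power of the planned analysis. They rest on the assumed splits, two equal jet groups and constant hazards; a 30/70 jet split changes the Cox limit with stone passage by at most 0.003. The unadjusted primary comparisons stand.

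**What to change.** In section 7.3, delete stone passage from the covariate list for both models. State that adjustment is limited to baseline variables known by the time of the RBUS, and list them: age, sex, BMI, side and CT stone size. Keep the explicit list, because section 5.2 allows the RBUS up to 10 days after CT and a stone could pass before it; such early passage should not enter as a covariate. If prior stone passage or stone location was meant, name that variable instead.

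The cost is one line of wording and no new data. It is best settled before the interim analysis at 50 patients, which may decide whether recruitment continues.

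Optional, and separate from the correction: add CT stone location, which section 1.1 cites as related to passage. Its three levels cost two parameters per model, or one net once stone passage is removed.

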1.0 BACKGROUND AND RATIONALE

1.1 Study Disease

Nephrolithiasis is a relatively common affliction, affecting upwards of 10% of the US population and accounts for a significant number of Emergency Department (ED) visits [1]. Computed tomography (CT) is the gold standard for evaluation of acute renal colic and diagnosis of urolithiasis [2] [3]. Recently, the use of CT has come under scrutiny due to ionizing radiation and its attendant risks, including skin injury, cataract formation, and most worrisome, solid and hematological malignancy [3][4, 5]. Furthermore, radiation exposure is increased in obese patients [6], a known risk factor for stone disease. Also, as many patients have a life-long affliction with nephrolithiasis[1], the potential for a considerable aggregate accumulation of radiation exposure over their lifespan can be excessive [5, 7, 8]. This patient population, especially those first diagnosed at a young age, would benefit from imaging modalities that do not involve radiation.

Therefore, various efforts are being made to reduce this radiation exposure. One of the most common types of imaging used in the evaluation of nephrolithiasis as an alternative to CT is renal and bladder ultrasound (RBUS) [9]. RBUS has largely been used as an adjunct study in the management of patients with nephrolithiasis[10], especially during pregnancy and in pediatric stone formers. Due to its relatively low cost and lack of radiation, it has the potential to have an increasingly prominent role. The incorporation of ureteral jets assessment (UJA) when using RBUS to assess patients with nephrolithiasis has been shown to have added diagnostic and possibly also prognostic value in the evaluation of these patients[10]. Several studies have attempted to assess the exact role of UJA in patients with nephrolithiasis but have had limited success in delineating its exact role in the treatment algorithm [11].

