2.0 OBJECTIVES

2.1 Primary Objective

1. To determine whether use of renal bladder ultrasound (RBUS) with UJA is predictive of spontaneous stone passage versus need for surgical intervention over a 42-day time frame.

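### The predictor is named as RBUS with UJA, but no grey-scale finding is pre-specified in the prognostic analysis, so the plan does not show whether jets predict outcome beyond hydronephrosis

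*Combined protocol and SAP*

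**What the plan says.** Section 2.1 sets the primary objective: "To determine whether use of renal bladder ultrasound (RBUS) with UJA is predictive of spontaneous stone passage", as against need for surgery, over 42 days. Section 7.1 repeats the same combined predictor. Section 1.2 narrows the question to the ipsilateral jet and hypothesises that a weak or absent jet indicates obstruction. Section 1.1 gives as background that adding UJA to RBUS "has been shown to have added diagnostic and possibly also prognostic value".

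Section 5.2 specifies what is read from each study scan:
- Hydronephrosis: "In addition, presence of hydronephrosis (mild, moderate, and severe) will be documented", with a definition for each grade.
- Hydroureter: "the presence or absence of hydroureter (proximal ureter, above the iliac bifurcation and distal ureter, below the iliac bifurcation) will be documented". This is present or absent at two levels, with no severity grade.
- Jets: "Patients will be categorized into three groups", and the three definitions use the jets alone.

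Section 7.3 then plans, for the primary objective:
- An unadjusted comparison of passage times: "Kaplan-Meier curve will be used to test time to spontaneous stone passage between the two groups".
- An unadjusted comparison of surgery, with the groups again left undefined, by a chi-square test.
- Cox and logistic models, described thus: "A multivariate analysis will also be conducted controlling for such variables as age, gender, BMI, side, size of stone, and stone passage".

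**The concern.** The named predictor has two parts, grey-scale findings and jets, and only the jets define a grouping. Hydronephrosis is a dilated collecting system by the definitions in section 5.2, and section 1.2 treats a weak or absent jet as a sign of obstruction. Two signs of obstruction from one scan can be expected to be correlated, so a jet association with outcome may partly or wholly repeat what the grey-scale read already shows.

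Two questions would be left open. If jets are associated with outcome, the planned analysis does not say whether the 5-minute jet observation adds to a scan without it. If they are not, it does not say whether RBUS predicts passage through its grey-scale findings, although these belong to the named predictor.

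**Working it through.** **1. Where the grey-scale findings are used.** Setting section 5.2 against section 7.3:

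| Item | Recorded (5.2) | Defines a group (5.2) | Named in 7.3, primary objective |
|---|---|---|---|
| Jets | yes | yes, three groups | as UJA |
| Hydronephrosis | yes, three grades plus absence | no | no |
| Hydroureter | yes, present/absent at two levels | no | no |

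Secondary objective 1 passes the RBUS results to a blinded urologist, but that concerns agreement with CT, not prognosis. Secondary objective 2 uses Cox models with unspecified factors and does not name either finding.

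**2. The plan's own figures.** The target of about 100 participants cannot be reproduced, because no alpha, power, event rate, effect size or group split is given. The point does not depend on it. The documents also give no hydronephrosis prevalence, no jet-hydronephrosis link and no intervention rate. What follows is therefore illustration on assumed inputs.

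**3. Crude jet association when jets add nothing.** Let h be the proportion with hydronephrosis, a and b the proportions with a weak or absent jet with and without it, and s1 and s0 the intervention rates with and without it. Given hydronephrosis, the jet has no effect. Then:
- P(hydro | weak) = ha / [ha + (1−h)b]
- P(hydro | normal) = h(1−a) / [h(1−a) + (1−h)(1−b)]
- Intervention rate in a jet group = s0 + (s1−s0) × P(hydro | that group)

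With h = 0.40 throughout:

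| Assumed link | a / b | s1 / s0 | P(hydro): weak / normal | Intervention: weak / normal | Crude OR |
|---|---|---|---|---|---|
| Weak | 0.50 / 0.30 | 0.35 / 0.20 | 0.526 / 0.323 | 27.9% / 24.8% | 1.17 |
| Moderate | 0.60 / 0.20 | 0.40 / 0.15 | 0.667 / 0.250 | 31.7% / 21.3% | 1.72 |
| Strong | 0.70 / 0.10 | 0.50 / 0.10 | 0.824 / 0.182 | 42.9% / 17.3% | 3.60 |

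Moderate row in full: P(hydro | weak) = 0.24/(0.24+0.12) = 0.667; P(hydro | normal) = 0.16/(0.16+0.48) = 0.250; rates 0.15+0.25×0.667 = 0.317 and 0.15+0.25×0.250 = 0.2125; OR = (0.317/0.683)/(0.2125/0.7875) = 1.72.

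Holding s1/s0 at 0.50/0.20 and changing only the jet link gives an OR of 1.30 (a/b = 0.60/0.40), 1.70 (0.70/0.30) and 2.24 (0.80/0.20).

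**4. How often a study of 100 would find it.** Simulation with 2,000 runs, two jet groups, binary hydronephrosis and two-sided 0.05: the crude chi-square is significant in about 7%, 23% and 80% of studies for the weak, moderate and strong links. The jet term in a logistic model that also contains hydronephrosis is significant in about 5–6%. These rates are approximate. The crude results are not false positives, since the jet groups do differ in outcome; they show how often a real crude association would appear without any added information.

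**5. Events per model term.** Assume 20–40% intervention, so 20–40 events in 100 participants, with one term per covariate and one or two terms for UJA.
- List as named: 6 + (1 to 2) = 7–8 terms; 20/8 = 2.5 to 40/7 = 5.7 events per term.
- Without stone passage: 6–7 terms; 20/7 = 2.9 to 40/6 = 6.7.
- Without stone passage, with one hydronephrosis term: 7–8 terms; again 2.5 to 5.7.
- List as named, with hydronephrosis and hydroureter added: 9–12 terms; 20/12 = 1.7 to 40/9 = 4.4.

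**The case against.** The strongest reply is that added value over grey-scale RBUS is not a stated objective. Sections 2.1 and 7.1 ask about RBUS with UJA as a package, section 1.2 asks about the jet, and the remark on added value in section 1.1 describes earlier work. For a prognostic marker, an unadjusted association is a proper answer even when another marker shares it. Conditioning on hydronephrosis changes the question rather than removing ordinary confounding. This stands, and it is why both results should be reported. It does not close the gap: if the package is the predictor, the jet groups do not test it, because they contain no grey-scale finding.

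A second reply is that the covariate list is illustrative. A reader might infer that hydronephrosis is excluded, or that a jet effect can never be separated from the grey-scale findings. The documents support neither: the list is open, and both findings are recorded on the study scan. What is missing is pre-specification.

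A third is that section 7.3 does not define its two groups, so reading them as jet groups is an inference. That is fair, although the three jet groups in section 5.2 are the only grouping of patients by scan result that the protocol defines.

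Finally, the size rests wholly on assumed rates, and with a weak link the consequence is negligible (about 7% crude against 6% adjusted). That also stands.

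**Conclusion.** The point holds as a gap in pre-specification. Grey-scale findings belong to the named predictor and are collected, but they have no stated role in the prognostic analysis. The plan therefore leaves the grey-scale part unevaluated for prognosis and does not show whether jets predict outcome beyond hydronephrosis.

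A reader might go further and infer that a positive jet result would be spurious. It would not: in every scenario above with a jet-hydronephrosis link, the jet groups truly differ in outcome. Only a claim that UJA adds to grey-scale RBUS would lack support.

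The size is unknown. A crude odds ratio of about 1.2 to 3.6 with no independent jet effect depends on assumed prevalence, link and intervention rates, two jet groups and binary hydronephrosis. The change is worth making because it is cheap and concerns the primary objective, and the data collected allow it.

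**What to change.** In section 7.3, primary objective:

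1. Tabulate stone passage and intervention by hydronephrosis grade beside the UJA groups.
2. Remove stone passage from the covariates. It is the outcome of the Cox model and nearly the complement of intervention in the logistic model; while it stays, the UJA coefficient cannot be interpreted with or without hydronephrosis.
3. Fit the Cox and logistic models for UJA with and without one hydronephrosis term, either ordinal or dichotomised at a cut fixed before the 50-patient interim analysis.
4. Report both. The model without the term addresses whether jets predict outcome; the model with it addresses whether they do so beyond hydronephrosis. Base any statement that UJA adds to grey-scale RBUS only on the latter.
5. State how the two groups in section 7.3 relate to the three in section 5.2, so that the UJA term is defined.

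The cost is one covariate already collected, one extra fit of each model and one table. The interval for the UJA effect will widen because the two findings are likely to be correlated. Events per term fall from 2.9–6.7 to 2.5–5.7 under the assumed 20–40% intervention, which is the same as for the list now named. With so few events, one grey-scale term is as much as the models should take on.
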